8.5 Preparation and storage of allocation list

The allocation responsible person (designated by the sponsor) shall create an allocation list.

Study subjects will be allocated at the Case Registration Center through the Case Registration Web System, using "the total score for the DTR-QOL Questionnaire [$<80\% (<168.2 \text{ as a score})$ or $\geq 80\% (\geq 168.2 \text{ as a score}^{\text{※}})$]" and "HbA1c ($<8.0\%$ or $\geq 8.0\%$)" at the start of the screening period as stratification factors. The Case Registration Center will use the allocation list for stratification prepared by the allocation responsible person in operating the treatment allocation.

※ Refer to the section 9.1.9 for the calculation method of the total score for the DTR-QOL Questionnaire.

Information on the allocation shall be kept in a safe place and shall not be available to anyone other than authorized persons, to secure independency from the clinical research.

9.0 CLINICAL STUDY PROTOCOL

9.1 Clinical study procedures

The principal investigator or investigator shall collect data in accordance with the procedure below. In principle, all the tests, observations, and evaluations of study subjects shall be performed by the same principal investigator or investigator with the exception of the specific 20-lipoprotein fraction. The study schedule is provided in Appendix A.

9.1.1 Informed consent

The procedures for obtaining informed consent are described in Section 15.3.

Consent shall be obtained from the study subject before initiation of study procedures.

A study subject ID code will be given to each study subject who provided informed consent, and then the study subject is to be de-identified. The study subject ID code shall be used throughout the study period and shall not be changed.

9.1.2 Demographic data and medical history

The following data will be collected as demographic data:

- Date of birth, sex, smoking history, alcohol intake history, the time (month and year) of diabetes onset (or a diabetes diagnosis)

As medical history, the information on clinically problematic diseases and symptoms resolved/recovered within a year before the start of the screening period will be collected. A continuous disease/symptom will be considered as a comorbidity.

9.1.3 Physical examination

The presence/absence of clinically significant abnormalities at subsequent physical examinations during the course of this study treatment will be determined compared with the baseline physical examination.

9.1.4 Body weight, height, and BMI

Body weight shall be measured to one decimal place in kilograms.

Height shall be measured to the nearest whole number in centimeters.

The sponsor will calculate BMI using the formula below, showing one decimal place.

Body Mass Index: $BMI = \text{body weight (kg)} / [\text{height(m)}]^2$

9.1.5 Concomitant drugs

Concomitant drugs are all drugs to be given in addition to the study drug or comparative drug. Drugs prescribed by physicians or the over-the-counter medicines purchased by the study subjects shall be included. At every visit of the study subject, any use of drugs (name, dosage/administration, route of

administration, duration of use, and intended use) shall be investigated and recorded on the CRF from the start of the screening period to the completion of the clinical study. In addition, the followings shall be recorded on the CRF; any use of therapeutic drugs for comorbidity *; number of daily doses of therapeutic drugs for comorbidities (<2 times or ≥ 2 times); and total number of daily tablets of therapeutic drugs for comorbidity (<2 tablets or ≥ 2 tablets) from the start of the screening period to the completion of the clinical study.

* For recording of any use of therapeutic drugs for comorbidity; number of daily doses of therapeutic drugs for comorbidity (<2 times or ≥ 2 times); and total number of daily tablets of therapeutic drugs for comorbidity (<2 tablets or ≥ 2 tablets), drugs for as-needed use and topical use and supplements are not be included. For drugs for once-weekly use, the numbers shall be divided by 7 for recording.

9.1.6 Comorbidities

A comorbidity shall be defined as a disease or symptom present at the start of the screening period or observed from the start of the screening period until before the start of study drug or comparative drug administration. Clinically problematic laboratory tests and abnormal physical examination findings, etc. observed through the first tests and physical examination at the start of the screening period shall be considered as comorbidities at the discretion of the principal investigator or investigator. The details of comorbidities (diagnoses) shall be investigated.

9.1.7 Laboratory tests

The laboratories will perform the tests shown below in accordance with the Schedule for Study Procedures (Appendix A). The tests will be performed under the ≥ 10 -hour fasting condition (excluding start of observation period). The principal investigator or investigator will retain the reported results of laboratory tests along with evaluating them..

Table 9.a Laboratory tests

Serum chemistry	
• HbA1c	• Glycoalbumin
• Fasting blood glucose	• 1,5-AG
• Fasting insulin	• serum creatinine
• Fasting glucagon	

Urinalysis	
• urinary 8-OHdG	• Urinary creatinine

The principal investigator shall keep laboratory test reference values, including the historical data.

9.1.8 The Basic Information on Study Subject (Your Basic Profile)

Study subjects will answer the "Your Basic Profile" regarding their diabetes therapy at each assessment time point during the screening period and treatment period. The principal investigator or investigator will provide directions to the study subjects to answer all questions truthfully and recorded the answer of each question on the CRF. Of note, in the column "Other drugs than diabetic drugs (e.g., for hypertension)" in the "Your Basic Profile", drugs prescribed in a medical institution shall be recorded. (Supplements and medicines for as-needed use are not included, even though it was prescribed in a medical institution.)

9.1.9 DTR-QOL Questionnaire

Subjects will answer the DTR-QOL Questionnaire (all 29 questions)⁵⁾ regarding the diabetes therapy being conducted at each assessment time point during the screening period and treatment period. The investigator will instruct the subjects to answer all questions truthfully and record the answer of each question of the DTR-QOL Questionnaire (29 questions in total) on the CRF.

[Calculation of the total score based on answers of the DTR-QOL Questionnaire]

- Calculation method of the total score of Factor 1: "burden on social activities and daily activities" (13 questions in all)

Every score of the question number 1-13 will be simply added up, and the total figure will be subsequently converted to percentage [the best (91) and worst (13) scores will be equivalent to 100% and 0%, respectively].

- Calculation method of the total score of Factor 2: "anxiety and dissatisfaction with treatment" (8 questions in all)

Every score of the question number 14 and 19-25 will be simply added up, and the total figure will be subsequently converted to percentage [the best (56) and worst (8) scores will be equivalent to 100% and 0%, respectively].

- Calculation method of the total score of Factor 3: "hypoglycemia" (4 questions in all)

Every score of the question number 15-18 will be simply added up, and the total figure will be subsequently converted to percentage [the best (28) and worst (4) scores will be equivalent to 100% and 0%, respectively].

- Calculation method of the total score of Factor 4: "treatment satisfaction" (4 questions in all)

Each score of the question number 26-29 will be converted into reverse (i.e., 1 will be converted to 7, 7 will be converted to 1, and so on. The converted scores, where 7 is the best and 1 is the worst, have the opposite sequence of the original scores). Then, the converted scores will be simply added up, and the total figure will be subsequently converted to percentage [the best (28) and worst (4) scores will be equivalent to 100% and 0%, respectively].

- Calculation method of the total score of all questions

Each score of the question number 26-29 will be converted into reverse, as described above, and then these converted scores and original scores of the question number 1-25 will be simply added up. Subsequently, the total figure will be converted to percentage [the best (203) and worst (29) scores will be equivalent to 100% and 0%, respectively].

If some answers of a questionnaire are unavailable (i.e., missing data), the scores will be handled in the manner below:

Factor 1-4: As for a factor associated with <50% missing data, the mean value calculated from available answers will be applied to cover the missing data.

The total score for a factor with $\geq 50\%$ missing data should not be calculated.

The total score of whole questions should not be calculated as well, if a total score of any of the four factors is unavailable.

9.1.10 DTSQ

Subjects will answer the DTSQ (all 8 questions)^{6), 7)} regarding the diabetes therapy being conducted at each assessment time point during the treatment period. The investigator will instruct the subjects to answer all questions truthfully and record the answer of each question of the DTSQ (8 questions in total) on the CRF.

9.1.11 Treatment Compliance

Throughout the study period, instructions for treatment will be given to subjects. If instructions were given for treatment incompliance, the details will be recorded on the source document. At each visit, the investigator will check with subjects the treatment compliance status with study drug or comparative drug.

The investigator will instruct the subjects to record study drug or comparative drug usage on a “Diabetes Treatment Medication Record Card*.” The subjects will also be instructed to bring empty sheets allowing compliance and usage to be checked along with the “Diabetes Treatment Medication Record Card*” at each visit. The treatment compliance status with the study drug or comparative drug (administration time and quantity of the study drug or comparative drug prescribed and unused) will be recorded on the CRF throughout the study period.

*: Diabetes Treatment Medication Record Card: The card contains an electronic circuit board, and the times that medication is taken are electronically recorded by pressing a button when medication is taken.

9.1.12 Hospitalization for type 2 diabetes

The investigator will check with study subjects any hospitalization for type 2 diabetes after the first administration of the study drug or comparative drug (excluding educational hospitalization without worsening of diabetes). The admission-discharge date will be recorded on CRF.

9.1.13 Contraception

Female subjects of childbearing potential (e.g., nonsterilized or premenopausal female subjects) must use adequate contraception from signing on the informed consent throughout the study period. At the time of acquisition of informed consent from an applicable study subject, signature on the informed consent should be acquired only after explanation is made about what is the adequate contraception and that the subject must avoid to be pregnant during the study period by use of the informed consent form until the subject thoroughly understands them.

9.1.14 Pregnancy

When a study subject or a partner of study subject was found to be pregnant during the study period, the principal investigator or investigator notify the monitoring staff of the sponsor. The principal investigator or investigator provide detailed information using the Follow-up Form for Pregnancy separately wherever possible.

9.1.15 Record of study subjects who are withdrawn before randomization

A CRF shall be created for all study subjects who have signed the consent form and withdrawn before randomization.

The following items are to be described on the CRF.

- Date of consent obtainment
- Date of birth
- Gender
- Eligibility
- Reason for discontinuation

The primary reason for withdrawal before randomization shall be recorded on the CRF according to the following classification:

- Not satisfying at least one of the inclusion criteria or meeting any of the exclusion criteria
- Major protocol deviation
- Lost to follow-up
- Voluntary discontinuation (specify the reason)
- Study termination
- Pregnancy
- Others (specify the reason)

Study subject ID codes assigned to study subjects withdrawn from the study before randomization shall not be reused.

9.1.16 Record of randomization

Study subjects to be randomized shall meet all of the inclusion criteria and shall not meet any of the exclusion criteria according to Section 8.4. The principal investigator or investigator shall specify the primary reason why the study subject cannot be randomized.

9.2 Implementation time point of the tests and observation

The schedule for all tests, observations, and evaluations is shown in Appendix A. The principal investigator or investigator shall perform the tests, observations, and evaluations at the time points shown below.

9.2.1 Screening period (Week -4)

After obtaining informed consent, the physical examination and tests will be performed for the determining eligibility for study enrollment. The eligibility of a patient will be determined based on the inclusion/exclusion criteria presented in the section 7.0. Refer to the section 9.1.16 for the preparation of records on a study subject withdrawn from the study before randomization.

Tests, observations and evaluations performed at the start of the screening period (Visit 1: Day -29 to -1) are shown below.

- Informed consent
- Inclusion/ exclusion criteria
- Demographic data, medical history
- Physical examination*
- Height, body weight and BMI
- Concomitant drugs*
- Comorbidity*
- Laboratory tests (HbA1c only) *
- DTR-QOL Questionnaire*
- The Basic Information on Study Subject (Your Basic Profile)*

*: To be performed during from Day -29 until Day -14.

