9.2.2 Treatment period (Week 0)

An eligible study subject in consequence of the tests, observations and evaluations before the start of the treatment period will be randomized in accordance with the section 8.4.

Tests, observations and evaluations performed at the start of the screening period (Visit 2: Week 0) are shown below.

- Inclusion/ exclusion criteria
- Physical examination
- Concomitant drugs
- DTR-QOL Questionnaire
- DTSQ
- The Basic Information on Study Subject (Your Basic Profile)
- Comorbidity
- Adverse event[#]
- Laboratory tests (blood chemistry and urinalysis)
- Hospitalization for type 2 diabetes[#]
- Prescription of the study drug/ or comparative drug

#: To be performed after the first administration (Day 1).

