2 EFFICACY EVALUATIONS	11
2.1 Primary Endpoint and the Analytical Methods	11
2.2 Secondary Endpoints and the Analytical Methods	11
2.3 Other Analysis	12
2.4 CONSIDERATIONS on STATISTICAL ANALYSIS	15
2.4.1 Adjustments for Covariates	15
2.4.2 Handling of Dropouts or Missing Data	15
2.4.3 Interim Analysis and Early Discontinuation	15
2.4.4 Multicenter Studies	15
2.4.5 Multiple Comparisons/Multiplicity	15
2.4.6 Use of an Efficacy Subset of Subjects	15
2.4.7 Active-Control Studies Intended to Show Equivalence	15
2.4.8 Subgroup Analysis	15
3 SAFETY EVALUATION	16
3.1 Treatment -Emergent Adverse Event	16
3.1.1 Brief Summary of Adverse Events	16
3.1.2 Display of TEAE	17
3.2 Frequency of Hypoglycemia	18

3.3 Hospitalization related to type 2 diabetes mellitus	18
4 LISTINGS.....	18
Significance level, Confidence coefficient	21
REVISION HISTORY.....	22

DEFINITIONS of TERMS

- Treatment -emergent adverse event (TEAE) : The AE which occurs after taking the first dose of trial medication.
- Summary Statistics: Number of subjects, mean, SDs, maximum values, minimum values, and quartiles
- BMI: Body Mass Index
- MedDRA: Medical Dictionary for Regulatory Activities
- QOL: Quality Of Life
- WHO: World Health Organization
- DTSQ: Diabetes Treatment Satisfaction Questionnaire
- DTR -QOL: Diabetes Therapy -Related QOL
- Subject with hypoglycemia: The subject with AE related to hypoglycemia
- Non Serious TEAE: Non -Serious TEAE is defined as Non -Serious TEAEs of at least 5% in any treatment group by SOC and PT. (if no event exceeds the 5% frequency, cutoff is lowered to 2%).

ANALYSIS SET

- Full Analysis Set
The subjects who were randomized and received at least one dose of the Trelagliptin or Daily DPP-4 inhibitor
- Safety Analysis Set
The subjects who received at least one dose of the Trelagliptin or Daily DPP-4 inhibitor

TIME WINDOW

For each assessment, observation and evaluation item, evaluable data is selected according to the following table. When there are multiple data exist within a time window, the one with the closest date to the reference date is adopted, and if the differences from the reference date are the same for multiple data, the later one is adopted.

1) DTR -QOL Questionnaire, The Basic Information on Study Subject, Laboratory Test (HbA1c)

Analysis Visit	Reference Date	Time Allowance (Number of Study Days)
Week -4	-30	-30～-15
Week 0	-1	-14～-1
Week 4	28	21～35
Week 12	84	70～97

Analysis Visit	Reference Date	Time Allowance (Number of Study Days)

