Planned Number of Dosage of Trelagliptin (tablets)	(The last administration date - the first administration date) / 7) +1. * Cut off to the whole number	All data must not be missing.
Planned Number of Dosage of Daily DPP -4 Inhibitor (tablets)	(The last administration date - the first administration date) \times number of daily dose \times number of tablets at the first administration date	All data must not be missing.
Study Medication Compliance (%)	Actual number of dosage / Planned number of dosage \times 100 (tablets)	All data must not be missing.
Days after Administration (Days)	Examination/observation/evaluation date - the first administration date +1	All data must not be missing.

Items	Method	Conditions
Duration of Diabetes (year)	$\{ (\text{The first administration date (year)} \times 12 + \text{The first administration date (month)}) - (\text{Onset Date of Diabetes (year)} \times 12 + \text{Onset Date of Diabetes (month)}) \} / 12$ (rounded off two decimal places)	All data must not be missing. If only the month of the onset of diabetes is unknown, the month of the onset of diabetes is regarded as "January".
8-OHdG/Creatinine (ng/mg CRE)	8-OHdG (ng/mL) / Urine creatinine (mg/dL) $\times 100$	All data must not be missing.

Display digit

Item	Defitintion
Mean, Confidence interval, Quartiles	Round statistics down to the 1 digits lower than significant digits of the data.
Standard Deviation	Round to the 2 digits lower than significant digits of the data.
Minimum and Maximum Values	Display the data at the significant digits.
Proportion, Percentage	Round to the one decimal place.
P-value	Round down to four decimal places. If p-value is less than 0.0001, display "p<0.0001"

AE related to Hypoglycaemia

AE related to Hypoglycaemia is defined as below.

PT Code	PT Name (Japanese)	PT Name (English)
10020993	低血糖	Hypoglycaemia
10040576	低血糖ショック	Shock hypoglycaemic
10065981	低血糖性意識消失	Hypoglycaemic unconsciousness
10048803	低血糖性痙攣	Hypoglycaemic seizure
10021002	低血糖性脳症	Hypoglycaemic encephalopathy
10021000	低血糖昏睡	Hypoglycaemic coma
10020997	無自覚性低血糖	Hypoglycaemia unawareness
10054998	神経低糖症	Neuroglycopenia

1 SUBJECTS, DEMOGRAPHIC and OTHER BASELINE CHARACTERISTICS

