2 EFFICACY EVALUATIONS

2.1 Primary Endpoint and the Analytical Methods

Analysis Set: Full Analysis Set

Items: Change from Baseline in DTR-QOL Total Score at End of Study (Week 12)

Method: Analysis of covariance (ANCOVA) is conducted to compare between the treatment groups using "Change from baseline in DTR-QOL total score by the end of treatment [the End of Study (Week 12) - baseline (Week 0)]" as a dependent variable; DTR-QOL Total Score at the start of the screening period(<80 or ≥ 80) and HbA1c ($<8.0\%$ or $\geq 8.0\%$) at the start of the screening period as covariates; and "treatment group" as an independent variable. The level of significance is defined as 5% (two-sided).

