2.4.2 Handling of Dropouts or Missing Data

Data which are not adopted as a result of data missing of each analysis item or data handling in accordance with this statistical analysis plan item will be excluded from the analysis target for the statistical test or estimation of the evaluation.

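### The protocol's screening window and the SAP's Week -4 window differ by a day, and SAP 2.1 does not name the source of its screening covariates, so subjects with known strata could be excluded

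*Protocol*

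**What the plan says.** **Protocol.** Section 9.2.1 marks the screening DTR-QOL and HbA1c with a footnote: "To be performed during from Day -29 until Day -14". The text is the same in both protocol versions supplied. In 9.2.2 the footnote beginning "To be performed after the first administration (Day 1" ties Day 1 to first administration. The protocol does not say whether a Day 0 exists. Section 8.5 allocates subjects using the DTR-QOL and HbA1c categories "at the start of the screening period as stratification factors", and sets no day window there.

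**SAP, Time Window, table 1** (DTR-QOL, Basic Information, HbA1c). Week -4 is -30 to -15 with reference day -30. Week 0 is -14 to -1 with reference day -1. If several records fall in one window, "the one with the closest date to the reference date is adopted".

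**SAP, Other Data Handling.** The only day formula, in the row for days after administration, is "Examination/observation/evaluation date - the first administration date +1".

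**SAP 2.1.** The primary ANCOVA adjusts for "DTR-QOL Total Score at the start of the screening period" (cut at 80) and for HbA1c at the same time point (cut at 8.0%). No data source is named. SAP 1.2.1 lists categories with the same cut points under the label Week -4.

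**SAP 2.4.2.** Data that are missing, or not adopted under the SAP's data handling, "will be excluded from the analysis target for the statistical test or estimation of the evaluation". There is no fallback.

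**The concern.** A screening record taken on the last permitted day, Day -14, meets the protocol but carries a day number that the SAP assigns to Week 0. The subject then has no Week -4 record. DTR-QOL and HbA1c share one window, so both screening values go together.

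Whether this reaches the primary analysis depends on something the SAP leaves open. If the programmer builds the two covariates from the windowed Week -4 record, the model has no values for this subject and SAP 2.4.2 removes them. If the programmer uses the stratum registered at allocation, nothing is lost.

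A second route to the same gap is a late start. SAP days are counted from first dose, and neither document limits the time from Visit 2 to first dose. A delay can move the screening record before Day -30, which is in no window.

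At stake is the avoidable exclusion of randomised, treated subjects who belong to the FAS, may have a complete primary outcome, and whose strata were fixed before treatment.

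**Working it through.** **1. The plan's sample size.** Inputs from Protocol 13.3: mean changes 19.0 and 14.4, so a difference of 4.6; SD 12.1; two-sided 5%; 80% power; 8% discontinuation. A two-sample t-test (noncentral t) needs 110 per group, with power 80.1%; the normal approximation gives 109. Then 110 / 0.92 = 119.6, rounded up to 120. The plan's figures reproduce. The expected evaluable number is 120 x 0.92 = 110.4 per group, so only 0.4 of a subject per group is spare.

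**2. The windows as days before first dose.** With a Day 0 (which the SAP's +1 formula creates), Day x is 1 - x days before first dose. Without a Day 0, Day x is -x days before.

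| Protocol numbering | SAP numbering | Protocol window (days before) | SAP Week -4 (days before) | Permitted days misfiled as Week 0 |
|---|---|---|---|---|
| Day 0 | +1 formula | 30 to 15 | 31 to 16 | 1 of 16 (Day -14) |
| no Day 0 | +1 formula | 29 to 14 | 31 to 16 | 2 of 16 (Days -14, -15) |
| no Day 0 | no Day 0 | 29 to 14 | 30 to 15 | 1 of 16 (Day -14) |
| Day 0 | no Day 0 | 30 to 15 | 30 to 15 | 0 of 16 |

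Under the SAP's stated formula (first two rows) the answer is 1 or 2 days of 16.

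**3. Late starters.** Suppose Visit 1 is 28 days before Visit 2 and the first dose is k days after Visit 2.

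- +1 formula: the screening day is -(28 + k) + 1 = -27 - k, which is below -30 when k is 4 or more.
- No Day 0: it is -28 - k, which is below -30 when k is 3 or more.
- With a 21-day gap the thresholds are 11 and 10 days. With a 14-day gap it does not happen within 14 days.

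In every row of the table the SAP window reaches at least as far back as the protocol's. A record too early for the SAP is therefore also too early for Protocol 9.2.1.

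**4. Effect on power.** Let f be the extra share lost, so n per group = 110.4 x (1 - f). The documents give no value for f; these are assumptions.

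| f | n per group | Power |
|---|---|---|
| 0 | 110.4 | 80.3% |
| 1% | 109.3 | 79.9% |
| 5% | 104.9 | 78.2% |
| 10% | 99.4 | 76.0% |

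**The case against.** The strongest reply is that SAP 2.1 never mentions Week -4 or the window table. It refers to the start of screening, as Protocol 8.5 does for the strata, and the protocol uses Week -4 simply as a name for Visit 1. On that reading the registered stratum is the covariate and nobody is lost. This stands as a possible reading, so loss from the primary analysis cannot be called certain. But the Time Window section says it selects the evaluable data for each item, SAP 1.2.1 uses the Week -4 label for these categories, and the SAP, listings included, never mentions the registered stratum. A programmer could reasonably take either route.

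Second, the two windows are equally long and exactly one day apart at both ends, which is what a numbering difference would produce. The +1 formula is labelled for days after administration. Applied before dosing, it puts the day before first dose at Day 0, which lies in no window. This also stands in part: 0 of 16 is possible. But that case needs the SAP windows to depart from the only formula the SAP states, so a convention still has to be written down.

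Third, the baseline outcome is largely protected. A Visit 2 record inside the Week 0 window lies nearer Day -1 than a Day -14 record and would be chosen over it. That is correct, but it does not restore the missing Week -4 values.

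Fourth, late starters breach the protocol's own window. This is right. For them the gap is the absence of a fallback, not a conflict between the documents.

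**Conclusion.** The printed windows conflict at the Day -14 edge, and the SAP leaves the source of the primary model's screening covariates unstated. Under the SAP's +1 formula, 1 or 2 of 16 permitted screening days are misfiled; under one alternative convention, none. Exclusion follows only if the windowed record supplies the covariates. Late starters are a separate, smaller point about a missing fallback.

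Three stronger readings are not supported:

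- **That affected subjects will drop out of the primary analysis.** They can; SAP 2.1 does not settle it.
- **That losses would differ by arm**, for example because users of a weekly drug choose a weekday for the first dose. The first dose does follow open-label allocation, but the documents give no delays by arm and no such rule.
- **That the 10 per group between 110 and 120 would absorb the loss.** That margin is already the 8% discontinuation allowance.

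The number affected cannot be derived, because the distributions of screening days and first-dose delays are not given. The effect on power is probably small, though with 110.4 expected against 110 needed, even an assumed 1% loss takes power just under 80%. The main reason to act is that a date rule should not remove treated subjects whose strata are known.

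**What to change.** - **SAP 2.1:** state that the two screening covariates are the DTR-QOL and HbA1c strata recorded in the Case Registration Web System at randomisation, whatever the date window. This also covers late starters.
- **SAP Time Window, table 1:** identify the Week -4 DTR-QOL and HbA1c record as the Visit 1 record. Failing that, state one study-day convention, including whether Day 0 exists, and align the Week -4 and Week 0 boundary with Protocol 9.2.1 under it.
- **Same table:** add that a Visit 1 record is never a candidate for Week 0.

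The cost is a few lines of SAP wording and bringing the registered stratum into the analysis dataset. No new data are needed.
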